## 5 EVENT SCHEDULE

### 5.1 Event Schedule – All Subjects

Procedure	Timepoint	Hospitalization			Inpatient or Outpatient Visits†				Safety Follow-up Visits	
		Phase	Screening *	Dosing *	Post-Dosing	Day 7 ± 1	Day 14 ± 1	Day 21 ± 1	Day 28 ± 1/ EOS	Day 42 ± 4
		Day 0 Pre-Dose	Day 0/1 Dose	Day 1 Post-Dose						
Informed Consent Form		X								
Eligibility Criteria		X								
Demographic Data		X								
Medical History 		X								
COVID-19 Signs and Symptoms		X		X	X	X	X	X	X 	X 
COVID-19 Complications				X	X	X	X	X		
Prior/Concomitant Medication		X			X	X	X	X		
Physical Examination		X			X 	X 	X 	X 		
Body Mass Index		X								
Vital Signs 		X		X	X	X	X	X		
Urine Pregnancy Test 		X								
Severity of COVID-19 (Ordinal Clinical Scale) 		X		X	X	X	X	X	X	X
Clinical Chemistry 		X							X 	
Serum Troponin I		X								
Hematology 		X							X 	
Urinalysis 		X							X	
Randomization			X							
Study Drug Administration 			X							
Adverse Events				X	X	X	X	X	X 	X 
Safety Follow-up									X 	X 

Coronavirus disease 2019 = COVID-19; EOF = end of follow-up; EOS = end of study

Note: Hospital can also refer to controlled facility such as an emergency room, urgent care facility, temporary/modular hospital, infusion center, clinical research unit, etc.

\* No more than 24 hours can elapse between screening and dosing with RBT-9.

† Day 7, 14, and 21 will be virtual visits; the Day 28 visit should be in person, but may be conducted virtually.

- 1 Medical history must include documentation of COVID-19 diagnosis.
- 2 On Days 42 and 56, COVID-19 symptoms (not signs) will be solicited.
- 3 Starting on Day 7, physical examination will be symptom-directed visual inspection.
- 4 Vital signs include assessment of blood pressure, pulse rate, oxygen saturation ( $\text{SpO}_2$ ), fraction of inspired oxygen ( $\text{FiO}_2$ ), and temperature.
- 5 Pregnancy testing is to be performed in female subjects of childbearing potential.

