## 9.7 Study Phase

### 9.7.1 Screening (Within 24 Hours Prior to Dosing)

Study candidates will be evaluated for study entry according to the stated inclusion and exclusion criteria ([Sections 9.1](#) and [9.2](#), respectively). The following procedures will be performed during Screening to establish each candidate's eligibility for enrollment into the study:

- Obtain signed, written informed consent. The informed consent must be signed before any procedures are performed.
- Record demographic information. The subject should also provide phone/email information for themselves and their closest relative so they can be contacted for virtual visits.
- Record medical history, including documentation of COVID-19 infection.
- Record COVID-19 signs and symptoms.
- Record concomitant medications, including previous treatment with anti-IL-6 therapies or Remdesivir.
- Perform physical examination, including calculation of body mass index.
- Record vital signs (blood pressure, pulse rate, SpO2, FiO2, and temperature).
- Obtain urine sample for pregnancy testing for female subjects of childbearing potential.
- Obtain blood samples for clinical chemistry, hematology, and troponin I testing.
- Obtain urine sample for urinalysis.
- Assess the severity of COVID-19 using the 8-point WHO Ordinal Clinical Scale (see [Section 9.10.5](#)).

The Investigator will evaluate the results of all examinations, including clinical laboratory tests, and determine each candidate's suitability for the study according to the eligibility criteria.

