### **9.7.3 Day 1 (Post-Dose)**

- Record COVID-19 signs and symptoms.
- Record COVID-19 complications.
- Record vital signs.
- Record severity of COVID-19.
- Solicit any adverse events.

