### **9.7.4 Visit Days ( $\pm 1$ ) 7, 14, 21, and 28/EOF**

All subjects will be assessed for the procedures listed below. For subjects who have been discharged from the hospital, visits will be conducted virtually (eg, by phone or video contact) on Days ( $\pm 1$ ) 7, 14, and 21. The visit on Day 28 should be conducted in person, but may be conducted virtually.

- Record COVID-19 signs and symptoms.
- Record COVID-19 complications.
- Record changes in concomitant medication.
- Perform physical examination, which will be symptom-directed visual inspection.
- Record vital signs.
- Assess the severity of COVID-19 using the 8-point WHO Ordinal Clinical Scale (see [Section 9.10.5](#))
- Obtain blood samples for clinical chemistry and hematology testing (Day 28 only).
- Obtain urine sample for urinalysis (Day 28 only).
- Solicit any adverse events.

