### **9.10.4 Vital Signs**

Vital signs (blood pressure, pulse rate, SpO2, FiO2, and body temperature) will be collected throughout the study at the timepoints defined in the Event Schedule (see [Section 5.1](#)).

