#### **11.1 Endpoints**

The following efficacy endpoints are defined for the study.

Primary Endpoint: Percentage of subjects in each treatment group in categories 4 through 8 of the 8-point WHO Ordinal Clinical Scale through Day 28.

Secondary Endpoints:

- Time to first occurrence of either death from any cause or new/worsened organ dysfunction through Day 28, defined as at least one of the following:
  - Respiratory decompensation
  - New or worsening congestive heart failure
  - Requirement of vasopressor therapy and/or inotropic or mechanical circulatory support
  - Ventricular tachycardia or fibrillation lasting at least 30 seconds and/or associated with hemodynamic instability or pulseless electrical activity, or resuscitated cardiac arrest

- Initiation of renal replacement therapy.
- Percentage of subjects who are alive at Day 28.
- Among subjects who begin oxygen therapy, mean change from initiation to last day on oxygen or Day 28 (whichever happens first) in SpO2/FiO2 ratio.
- Percentage of subjects with fever through Day 28.
- Percentage of subjects who develop AKI, as determined by the Investigator, through Day 28.
- Percentage of subjects with new or worsening congestive HF through Day 28.
- Percentage of subjects with ventricular tachycardia or fibrillation lasting at least 30 seconds and/or associated with hemodynamic instability or pulseless electrical activity, or resuscitated cardiac arrest through Day 28.
- Percentage of subjects who remain hospitalized at Day 28.
- Length of hospitalization through Day 28.
- Number of oxygen-free days through Day 28.
- Percentage of subjects transferred to the ICU through Day 28.
- Number of days on mechanical ventilation through Day 28.
- Time to and duration of vasopressor or inotrope utilization through Day 28.
- Percentage of subjects who begin dialysis through Day 28.

Exploratory Endpoints:

- Duration of COVID-19 symptoms through Day 56

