## 11.3 Data Analysis

The primary efficacy endpoint will be mapped to a binary endpoint (% categories 4-8) and then will be analyzed using a two-sided Fisher Exact test and using a logistic regression model to control for the stratification factors; the method of Firth will be used to predict outcomes. A two-sided Wilcoxon rank sum test will be used to compare the primary efficacy endpoint distributions for the two treatment groups. Continuous endpoints will be evaluated using a mixed model repeated measures (MMRM) analysis using a compound symmetry (CS) error structure. Time to event outcomes (eg, extubation, WHO progression, death) will be displayed using a Kaplan-Meier (KM) lifetable and treatment distributions compared using a stratified log-rank test and Cox proportional hazards model to control for time since COVID-19 diagnosis.

When appropriate, summary statistics will be provided (number of non-missing values, mean, median, standard deviation, minimum, and maximum for continuous variables and number and percentage of patients for categorical variables) by treatment group for all measures, including demographic and baseline assessments, safety, and efficacy endpoints. Baseline for all safety and efficacy endpoints is defined as the last observations before administration of study drug. No imputation will be used for missing data.

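### SpO2/FiO2 is not scheduled at oxygen start or on the last oxygen day, so the change endpoint lacks both anchor values for most oxygen courses

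*Combined protocol and SAP*

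**What the plan says.** Section 11.1 (repeated in the Section 4 synopsis) restricts the endpoint to a subgroup, "Among subjects who begin oxygen therapy", and defines it as the "mean change from initiation to last day on oxygen or Day 28 (whichever happens first") in SpO2/FiO2. Each subject therefore needs two dated values, and the dates follow the oxygen course, not the visit calendar.

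The only stated source of these values is the vital-signs assessment. Footnote 4 of the Event Schedule (Section 5.1) begins "Vital signs include assessment of blood pressure, pulse rate, oxygen saturation" and goes on to list FiO2. Section 9.10.4 says that vital signs "will be collected throughout the study at the timepoints defined in the Event Schedule". Those timepoints are:

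- Screening (Section 9.7.1);
- Day 1 after dosing (Section 9.7.3: "Record vital signs");
- Days 7, 14, 21 and 28, each ±1 day (Section 9.7.4).

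For discharged subjects, "visits will be conducted virtually (eg, by phone or video contact) on Days" 7, 14 and 21. Section 11.3 adds: "No imputation will be used for missing data".

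No section asks for a reading when oxygen starts or stops, a daily reading while on oxygen, or retrieval of charted readings. Section 9.10 promises regular monitoring but names no such record. Section 9.10.2 singles out antipyretics, vasopressors and inotropes, not oxygen. The ordinal scale (Section 9.10.7) is scored at the scheduled visits from the first assessment of the day, so it does not date the start or end of oxygen.

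**The concern.** Oxygen starts and stops on clinical need, while readings are taken on fixed days up to a week apart. A course from Day 2 to Day 6 contains no nominal visit. One from Day 3 to Day 12 contains a single visit, Day 7, which is neither its first nor its last day. Without imputation, such subjects have no endpoint value.

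Two things are at stake. First, the endpoint may rest on a small and unrepresentative part of the subjects it describes. Second, if analysts fall back on whichever visits happen to fall during oxygen, having two readings will depend on how long the course lasted. Course length is a post-randomization outcome that the drug is meant to influence, so the comparison could be distorted.

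A related gap is the starting value for subjects who enter on oxygen. The risk factors in Section 9.1 allow a saturation of 90 to 95% with supplemental oxygen, so initiation can precede every study reading. Section 11.3 sets baseline for all efficacy endpoints as the last pre-dose observation, which is a different anchor from initiation. The plan does not say whether these subjects are in the endpoint.

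**Working it through.** The plan states no figure for this endpoint, so there is none to reproduce. The check is a count of oxygen courses against the schedule.

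**Inputs.** Nominal vital-sign days after dosing are {1, 7, 14, 21, 28} (Sections 5.1, 9.7.3, 9.7.4). A course has start day s and last day e, with 1 ≤ s < e ≤ 28. Courses running past Day 28 end at e = 28, as the definition directs. One-day courses are left out. Adding Screening as Day 0 changes none of the counts below, because they concern starts on or after Day 1.

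**Step 1: all possible pairs.** Number of pairs: 28 × 27 / 2 = 378. Both days on a nominal visit: 5 × 4 / 2 = 10. Share: 10 / 378 = 2.6%.

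**Step 2: oxygen starting on Day 1.** Possible last days are 2 to 28, so 27. Those on a visit are 7, 14, 21 and 28, so 4. Share: 4 / 27 = 14.8%. For starts on Days 2 to 6, none of the 5 start days has a nominal reading.

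**Step 3: generous bound for visit windows.** Count every day inside a ±1 window as measured. Up to Day 28 this gives 12 days: 1, 6–8, 13–15, 20–22, 27 and 28. Pairs: 12 × 11 / 2 = 66, and 66 / 378 = 17.5%. Day 1 starts: 11 / 27 = 40.7%. Each visit takes place on only one day of its window, so the real share is lower.

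**Step 4: sensitivity to the course distribution (assumed, since the documents give none).** The number of days from start to last day, k, is geometric with mean m: P(k) = (1/m)(1 − 1/m)^(k−1), with m = 3, 5, 7, 10 or 14, cut off at Day 28. Starts not on Day 1 are spread evenly over Days 2 to 10. Example with m = 7 and a Day 1 start: last day 7 (k = 6) 6.6%, Day 14 (k = 13) 2.2%, Day 21 (k = 20) 0.8%, Day 28 or later (k ≥ 27) 1.8%, in total 11.4%.

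| Start timing | Both values, nominal days | Both values, ±1-window bound |
|---|---|---|
| None on Day 1 | 0.3–3.3% | 13.3–17.8% |
| Half on Day 1 | 2.5–13.8% | 14.1–31.2% |
| All on Day 1 | 4.7–24.2% | 14.8–44.6% |

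The ranges run over m = 3 to 14. Even in the most favourable cell, 100 − 44.6 = 55.4% of courses lack at least one anchor.

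**The case against.** The strongest reply is that the Event Schedule need not be the full data-capture specification. Other Section 11.1 endpoints, such as oxygen-free days, ventilator days, length of hospitalization and vasopressor timing, cannot come from weekly snapshots either, so the protocol seems to presuppose interval data from the chart. Section 9.4 provides for source documents and eCRFs, Section 11 defers data handling to a separate SAP, and Section 13 defers to a Data Management Plan. Neither of those plans nor the eCRF is in the reviewed text, and hospitals usually chart these readings.

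Part of this stands. The documents do not show that the endpoint is impossible, only that its capture is not specified. But a later analysis rule cannot create readings that sites were never asked to record. Retrospective retrieval could vary across up to 25 sites and would be done by staff who know the allocation, since Sections 9.6 and 10.5 make treatment open-label.

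A reader might also infer that the endpoint fails for nearly all courses. That is fair for oxygen begun after Day 1 on nominal days. It softens to most when courses start on Day 1 or windows are counted generously.

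A reader might go further and infer a bias against RBT-9 of a known size, because a drug that shortened oxygen would remove its own successes. The documents do not support this. Take starts spread evenly over Days 1 to 14. Under the written definition, 7-day and 14-day courses are equally evaluable, at 1 of 14 starts each. A contrast appears only if any two visits during oxygen are accepted, a rule the plan never states. Even then, comparing 14-day with 7-day courses, it is 14/14 against 1/14 for those even starts, 3/3 against 1/3 for even starts on Days 1 to 3, and no difference for Day 1 starts, where a 7-day course covers Days 1 and 7.

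Finally, the virtual visits matter little here. Sections 9.3 and 9.7.4 limit them to discharged subjects, and the scale places oxygen use in hospital. The Event Schedule footnote is looser.

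**Conclusion.** The mismatch is real: the endpoint is anchored on the first and last oxygen days, and the protocol schedules no reading on either. Followed as written, the schedule leaves most oxygen courses without both values under every start timing, duration and window assumption tested. The pair counts weight all start/last-day combinations equally and describe coverage of the calendar, not an expected missing rate. The expected rate depends on an oxygen-course distribution that the documents do not give.

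Distortion is possible if substitute visits are used, but neither its direction nor its size is established, and no single figure should be quoted. The problem concerns one secondary endpoint and does not affect the primary test, the interim rules or the sample size. It should be corrected because the values can be had cheaply now and may be patchy later.

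**What to change.** Add an oxygen log, filled from the hospital chart, to Section 9.7, Section 9.10.4 and the eCRF. It should hold:

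- the date and time of each oxygen start and stop;
- the charted SpO2 and FiO2 at the start;
- the charted SpO2 and FiO2 at the last reading on oxygen, or on Day 28 if oxygen continues.

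State in Section 11.1 whether subjects already on oxygen at Screening belong to the endpoint and, if so, which value is their starting value, and reconcile this with the baseline definition in Section 11.3.

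With both readings logged, all 378 pairs become computable, against 10 now. The same log supplies the dates for oxygen-free days. The cost is modest data entry and a few lines of protocol text, with no change to care.

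Moving the endpoint to fixed visits, such as Screening to Day 7, would avoid new fields. It would also ask a different question and lose recovered, discharged subjects who have no oximeter reading, so it is not a substitute.

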A standardized approach to treating patients with COVID-19 has been proposed based on the 3 grades of severity that correspond with clinical findings, response to therapy, and clinical outcome [Siddiqi 2020]. Stage I is considered to be mild in severity and corresponds to early infection. It is at this stage that viral incubation occurs, with patients experiencing mild, non-specific symptoms, such as fever, malaise, and dry cough. Stage I is the optimal time for treatment with agents that have antiviral activity, enhance viral clearance by the innate immune response, and protect organ function, so that progression of the disease is halted and recovery is undeterred.

Stage II is considered to be moderate in severity and corresponds to pulmonary involvement with or without hypoxia [Siddiqi 2020]. At this stage of severity, patients need to be hospitalized, as viral pneumonia develops and bilateral infiltrates or ground glass opacities are observed in the lungs; increasing lymphopenia is also observed, as

well as transaminitis. Once hypoxia sets in, mechanical ventilation and anti-inflammatory treatment is warranted; antiviral therapy remains a mainstay of treatment.

Stage III is considered to be severe and corresponds to systemic hyperinflammation [Siddiqi 2020]. Cytokine storm is in full effect, and acute respiratory distress syndrome, shock, cardiac failure, and renal failure can manifest. Antiviral therapy should continue, and anti-inflammatory agents should be tailored to prevent multi-organ dysfunction.

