## 6.2 Study Drug

RBT-9 (stannous protoporphyrin) is an agent that preconditions the body to combat insult and injury by eliciting an early stressor response, which subsequently boosts cytoprotective, anti-inflammatory responses that preserve functional and structural organ integrity. In addition to broad organ protection, RBT-9 possesses antiviral activity, which has been demonstrated against several enveloped viruses.

In Phase 1 clinical development conducted by Renibus, Therapeutics, Inc., RBT-9 has been shown to be safe and well tolerated. It was also shown to upregulate the cytoprotective/anti-inflammatory pathways (ie, nuclear factor erythroid 2-related factor 2 [Nrf2], interleukin-10 [IL-10]) that were identified in preclinical studies. RBT-9 is administered as a single dose via intravenous infusion over a 120-minute period. An immediate stressor response is induced, which converts to an antioxidant/anti-inflammatory state within 24 to 48 hours. The antiviral activity of RBT-9, as measured in vitro, has been observed to occur within 24 hours.

The COVID-19 pandemic has now spread to 192 countries and all 50 states in the United States. Treatments that can prevent the progression COVID-19 once a diagnosis has been made (ie, Stage I, early disease) are of critical need. If high-risk patients could be offered early treatment that prevents disease progression and preserves organ function, it would lead to a reduction in ICU admission rates, which may help “flatten the curve” of healthcare utilization.

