### 7.2 Secondary Objective

The secondary objectives are to evaluate the effect of RBT-9 versus placebo on the following through Day 28:

- Time to first occurrence of death from any cause or new/worsened organ dysfunction
- All-cause survival
- SpO2/FiO2 ratio
- Fever incidence
- AKI incidence
- New or worsening CHF
- Hospitalization status
- Length of hospital stay
- Oxygen-free days
- ICU status
- Days on ventilator
- Time to and duration of vasopressor or inotrope utilization
- Ventricular tachycardia or fibrillation lasting at least 30 seconds and/or associated with hemodynamic instability or pulseless electrical activity, or resuscitated cardiac arrest
- Dialysis status
- Safety parameters

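### The fever endpoint is not limited to new fever or adjusted for fever at baseline, so fever persisting from before the infusion into Day 1 counts as an event

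*Combined protocol and SAP*

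**What the plan says.** Section 7.2 lists "Fever incidence" through Day 28 as a secondary objective. Section 11.1 and the synopsis turn this into "Percentage of subjects with fever through Day 28". Neither place gives a temperature cut-off, a start for the counting window, a new-onset condition or a rule for subjects already febrile at entry.

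Three other endpoints in the same list do carry an onset condition. For kidney injury the wording is "Percentage of subjects who develop AKI, as determined by the Investigator, through Day 28". For heart failure the list has "Percentage of subjects with new or worsening congestive HF through Day 28", and for renal support it has "Percentage of subjects who begin dialysis through Day 28".

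Other relevant provisions:

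- **Baseline (11.3):** "Baseline for all safety and efficacy endpoints is defined as the last observations before administration of study drug". This general definition is not linked to how fever is counted.
- **Population:** section 6.1 describes early disease as "patients experiencing mild, non-specific symptoms, such as fever, malaise, and dry cough". No exclusion in section 9.2 removes febrile patients.
- **Measurements (5.1, 9.7.1, 9.7.3, 9.7.4):** temperature is taken at Screening, on Day 1 after the dose, and on Days 7, 14, 21 and 28.
- **Adjustment (11.3, 11.4):** the logistic model is for the primary endpoint and controls for the randomization stratum, time since diagnosis. Baseline fever appears in no model.
- **Adverse events (11.5, 9.10.5):** the rule excluding conditions present at baseline covers adverse events only, and COVID-19 signs and symptoms are kept out of adverse event reporting.

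**The concern.** Incidence means new cases. The endpoint as worded also takes in fever that began before treatment and was still present at the first post-dose reading. Three records show the effect, taking 38.0 °C as the cut-off for illustration only:

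| Record | Screening | Day 1 post-dose | Day 7 onward | Scored as |
|---|---|---|---|---|
| A | 38.6 | 38.4 | afebrile | fever |
| B | 36.8 | afebrile | new fever on Day 7 | fever |
| C | febrile | febrile | febrile through Day 14 | fever |

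Record A had no new fever and recovered, yet it scores the same as B and C. Carried-over fever of this kind should be about equally common in the two arms, so it adds events that say little about treatment and pulls the two percentages together. At stake is whether this secondary endpoint answers its own objective.

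**Working it through.** **The plan's own figures.** No rate, effect or power is stated for fever. The only power figures are for the primary endpoint (section 11.6: 84 placebo, 168 RBT-9, two-sided 0.045). A pooled chi-square calculation without continuity correction gives 84.9%, 85.6% and 84.6% for 25% vs 10%, 32% vs 15% and 38% vs 20%, against the stated 84%, 85% and 84%. The figures reproduce and confirm the group sizes, but say nothing about fever.

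**Dilution formula.** Let d be the fraction of each arm febrile at baseline and still febrile on Day 1, and q the probability of fever after Day 1 in the remaining subjects. Then

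- rate as written = d + (1 − d)q
- risk difference = (1 − d)(q placebo − q RBT-9)

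The factor (1 − d) is algebra. It requires d to be equal in the arms and unaffected by treatment.

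**Illustration 1.** Assumptions, none of them from the documents: q = 25% placebo and 12.5% RBT-9; 20–60% febrile at Screening; 60–80% of these still febrile on Day 1; two-sided Fisher test at 0.05 with 84 and 168 subjects, exact power.

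| Febrile at Screening × still febrile Day 1 | d | Placebo | RBT-9 | Difference (points) | Power |
|---|---|---|---|---|---|
| none carried over | 0 | 25.0% | 12.5% | 12.5 | 66% |
| 0.2 × 0.6 | 0.12 | 34.0% | 23.0% | 11.0 | 43% |
| 0.4 × 0.8 | 0.32 | 49.0% | 40.5% | 8.5 | 23% |
| 0.6 × 0.8 | 0.48 | 61.0% | 54.5% | 6.5 | 15% |

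Middle case in full: 0.32 + 0.68 × 0.25 = 0.490; 0.32 + 0.68 × 0.125 = 0.405; difference 0.085. Of the subjects counted, 0.32/0.490 = 65% on placebo and 0.32/0.405 = 79% on RBT-9 are already events on Day 1. Across the range this share runs from 0.12/0.34 = 35% to 0.48/0.545 = 88%.

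**Illustration 2.** This shows what restricting to subjects afebrile at baseline preserves. New-fever rates are assumed to be 25% vs 10% (borrowed from the primary sample-size table), a fraction f is febrile at baseline and all of them are counted, and power is by chi-square at 0.05.

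| f | Difference if counted (points) | Power if counted | Power, afebrile at baseline only |
|---|---|---|---|
| 0 | 15.0 | 86% | 86% |
| 10% | 13.5 | 66% | 82% |
| 20% | 12.0 | 49% | 78% |
| 30% | 10.5 | 36% | 73% |
| 50% | 7.5 | 20% | 59% |

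Under these assumptions, counting carried-over fever costs more power than the smaller denominator does.

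**The case against.** - **A reader might infer that any fever before the infusion scores as an event.** The documents do not support that. Under 11.3 a pre-dose temperature is baseline, and the objective is incidence. Record A scores only because of its second, post-dose reading. The defect is confined to fever that persists to a post-dose reading.
- **Section 11 defers data handling to a separate SAP, which might hold the rule.** It might, but no such rule is in the text supplied. A general deferral does not repair an endpoint whose wording departs from its objective.
- **The wording may be shorthand.** The ventricular arrhythmia endpoint in the same list has the same form and no onset word. That is fair, but fever is a presenting symptom of the disease under study, so here the shorthand changes the count.
- **It is tempting to say the drug gets no credit in subjects who enter febrile.** That goes too far. Under the assumptions above, 20–40% of them are afebrile by Day 1 and can finish without an event. Symptom duration through Day 56 is also a separate exploratory endpoint.
- **It is also tempting to say a Day 1 temperature cannot show benefit.** Section 6.2 states "An immediate stressor response is induced, which converts to an antioxidant/anti-inflammatory state within 24 to 48 hours", which makes early benefit less likely. But the same section reports in vitro antiviral activity within 24 hours, and no clock time is set for the Day 1 reading. If the early stressor response affects temperature, Day 1 fever could be a drug effect. This is a reason to keep that reading in view.
- **The size rests on assumed rates.** This stands. The undiluted 66% is itself sensitive: it would be 42% at 15% vs 7.5% and 29% at 10% vs 5%.

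**Conclusion.** The mismatch between objective and endpoint is real, and nothing in the supplied text closes it. As written, fever persisting from baseline to the Day 1 post-dose reading counts as an event in either arm, and the risk difference shrinks by (1 − d) if d is balanced and unaffected by treatment. Under the first set of assumptions the difference falls from 12.5 to 6.5–11 points and Fisher power from about 66% to 15–43%. These figures show scale and do not forecast this trial, because the documents give neither the share febrile at entry nor any fever rate. A reader might conclude that a powered comparison is being lost, but the plan claims no power for fever, which is one of many secondary endpoints. The primary conclusion is unaffected. The correction is still worth making, because it is cheap and the assignment is open-label (9.6, 10.5): a counting rule chosen later could look data-driven.

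**What to change.** In section 11.1 and the synopsis, replace the fever endpoint with wording to this effect:

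> Percentage of subjects with fever (temperature at or above a stated cut-off) at any assessment after the start of infusion through Day 28, analysed by Firth logistic regression adjusting for fever at baseline (last pre-dose temperature) and the randomization stratum. New-onset fever will be reported among subjects afebrile at baseline. Persistence or resolution will be reported separately among subjects febrile at baseline.

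The sponsor should supply the cut-off. Adjustment compares subjects of like entry status but does not remove carried-over fever from the count. The new-onset analysis is the one that matches the objective.

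Keep the Day 1 post-dose reading and do not start counting only at 48 hours. After Day 1 the scheduled temperatures are weekly, with virtual visits on Days 7, 14 and 21 for discharged subjects. A 48-hour start would drop the only scheduled early post-dose reading and could hide early drug-related fever.

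The cost is a little more analysis and a smaller denominator for the new-onset comparison. No visit or measurement is added, since pre-dose temperature is already collected. The wording should be settled before fever is compared by arm.
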